2.1.2 Reporting Conventions

The formats for the tables, listings, and figures described in this SAP will be provided in a companion document. Changes to the formats of these reports that are decided after the finalization of the SAP will not require an amendment. In addition, any additional supportive or exploratory analyses requested after SAP approval will not require amendment of the SAP. These additional analyses will be described in the CSR.

All study data from the eCRFs as well as derived variables will be provided in subject data listings. An indication of specific listings for each data type will not be indicated in the text of subsequent SAP sections. Data listings supplied as part of the CSR will be sorted by study center number concatenated with subject number, assessment dates, and/or time point.

The following conventions will be applied to all data presentations and analyses:

 GALDERMA	Title 43USSA1705ext SAP	Doc id
--	-----------------------------------	--------

Statistical Analysis Plan, Version 1.0 FINAL, 10 AUG 2020

- Quantitative variables will generally be summarized by the number of subjects, mean, standard deviation, median, minimum, and maximum. Unless otherwise specified, the minimum and maximum values will be displayed to the same number of decimal places as the raw data, the mean and median will be presented to one extra decimal place compared to the raw data, and the standard deviation will be displayed to two extra decimal places compared to the raw data
- Categorical variables will be summarized by the number and percentage of subjects (and number of events where appropriate) within each category. Unless otherwise specified, the percentage will be presented in parentheses to one decimal place. Frequency and percentage values of 0 will be presented as '0' rather than '0 (0)'.
- All summary tables will include the number of subjects.
- Date variables will be formatted as DDMMMYYYY for presentation.

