2.3.1 Subject Disposition

The number of subjects enrolled will be shown in total and by study center.

The disposition of subjects will be summarized, including numbers of subjects who were:

- Completed,
- Withdrawn (including primary reason for withdrawal).

These numbers will be summarized by study center. The number of subjects expected, completed, missed, and withdrawn will be summarized by scheduled visit.

- Expected = all subjects minus withdrawn subjects.
- Completed = subjects that showed up at that visit.
- Missed = expected subjects minus completed subjects.
- Withdrawn = all subjects who have withdrawn up to that visit.

All withdrawn subjects will be listed individually, by subject number, date and reason for withdrawal, and last visit performed.

Statistical Analysis Plan, Version 1.0 FINAL, 10 AUG 2020

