2.4.2 Handling of Missing Data

The number of missing values will be summarized and reported as appropriate.

All effectiveness endpoints will be evaluated based on Observed Cases.

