2.5 Safety Analysis

Safety endpoints will be summarized using descriptive statistics using the Observed Cases. There are no planned inferential statistical analyses of safety endpoints.

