2.5.1 Adverse Events

All AEs will be coded according to MedDRA and summarized by system organ class (SOC) and preferred term (PT).

A summary of all AEs (number and percentage of subjects with at least one event and number of events) will be provided, which will include:

- Subjects with at least one AE (in total as well as serious AEs).
- Subjects with at least one study product or injection procedure-related AE (in total as well as serious AEs).
- Subjects with at least one unrelated AE (in total as well as serious AEs).
- Number of subjects who did not have an AE.

Statistical Analysis Plan, Version 1.0 FINAL, 10 AUG 2020

The number of subjects with AEs related to study product or injection procedure as well as the number of events will be summarized by SOC, PT, and severity.

In addition, for related AEs the number of days to onset from last treatment (in the 43USSA1705 study) and the duration of event will be summarized by SOC and PT using mean, SD, min, max and median.

- Time to onset of an AE will be derived as the start date minus the date of the most recent treatment. If the start date is missing, it will be assumed that the AE started on the first day of the extension study.
- Duration of an AE will be derived as the stop date minus the start date + 1. Missing stop dates will not be imputed and therefore no duration will be calculated in these cases.

Action taken for related AEs will also be summarized. Non-related AEs will be summarized by SOC, PT, and intensity.

These summaries will be performed for:

- The whole period from baseline [REDACTED] to the end of the extension study [REDACTED]
- The period from baseline to the end of the 43USSA1705 study ([REDACTED])
- The period from start of the extension study [REDACTED] to the end of the extension study [REDACTED]

Serious AEs that starts during the extension study will be listed.

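### Duration of related AEs is summarised only for events with a stop date, with no count or minimum length shown for the rest, so it will tend to read short if any remain unresolved

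*SAP*

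**What the plan says.** SAP 1.6 names four components of the safety endpoint: incidence, intensity, time to onset and duration. For related AEs, SAP 2.5.1 says that "the duration of event will be summarized by SOC and PT using mean, SD, min, max and median". Duration is stop date minus start date plus 1, and where the stop date is absent: "Missing stop dates will not be imputed and therefore no duration will be calculated in these cases".

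Other provisions that bear on the point:

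- SAP 2.5.1, on related AEs: the number of subjects "as well as the number of events will be summarized by SOC, PT, and severity".
- SAP 2.4.2, under effectiveness: "The number of missing values will be summarized and reported as appropriate".
- SAP 2.1.2: "All summary tables will include the number of subjects", and "All study data from the eCRFs as well as derived variables will be provided in subject data listings". Table formats are left to a companion document.
- SAP 2.3.1: "All withdrawn subjects will be listed individually, by subject number, date and reason for withdrawal, and last visit performed".
- SAP 2.5: "There are no planned inferential statistical analyses of safety endpoints".
- Protocol 7.2.6: related events ongoing at study end are followed past the last visit until they resolve, are judged chronic or stable, or contact is lost. The information goes on an AE follow-up form.

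The text of Protocol 10.5 (safety analysis) and the companion table formats cannot be seen. SAP 2.1 gives the SAP precedence over the protocol's statistical sections where they differ.

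**The concern.** An event gets a stop date only if it ends while someone is still recording it. Dropping undated events therefore tends to drop the long ones, which matter most in a study of long-term safety. A mean printed without the number of omitted events can be read as the duration of all related AEs.

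The other provisions do not close the gap in the duration table:

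- The missing-value count in 2.4.2 belongs to effectiveness.
- The number of subjects in each table is not a number of events. A subject with one dated and one undated event under the same PT is still counted.
- The listings and the event counts by SOC, PT and severity would let a reader work out what was omitted, but only by reconciling separate outputs.
- Protocol 7.2.6 reduces the problem, but follow-up can end with an event chronic, stable or lost. The documents do not say how such events are dated, or whether stop dates from the follow-up form enter the derivation.

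Resolved events with an unknown stop date drop out too. For those, the direction of any bias is unknown.

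**Working it through.** The plan gives no figure for duration or for undated events, so there is nothing to reproduce. The check has three parts: direction, a bound without distributional assumptions, and a model range.

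**Direction.** Suppose a stop date is recorded only when duration D is no longer than the available follow-up C, with C independent of D. Recorded durations then have density proportional to f(t)·P(C ≥ t). This puts less weight on long durations than f(t), so mean and median are both shifted downward.

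**Bound.** Let a share q of related events be ongoing with mean minimum observed duration L, and let the dated events have mean r. The mean over all of them is at least (1 − q)r + qL. Understatement is certain only if L > r. The bound covers ongoing events, not resolved events of unknown date. Assumed: 20 related events, r = 20 d.

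| Ongoing events | Lower bound for the overall mean |
|---|---|
| 1 at 100 d | (19×20 + 100)/20 = 24 d |
| 1 at 300 d | (19×20 + 300)/20 = 34 d |
| 2 at 300 d | (18×20 + 600)/20 = 48 d |
| 1 at 10 d | (19×20 + 10)/20 = 19.5 d (shows no direction) |

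The SAP reports by SOC and PT, so cells may be smaller. With four dated events of 10, 20, 30 and 40 d (mean and median 25 d) and one ongoing at 300 d, the mean over all five is at least (100 + 300)/5 = 80 d and the median is 30 d. The mean is the exposed statistic.

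**Model range.** Durations are exponential with mean m, onset is uniform over the first W days of a period of T days, and there are no stop dates after T. With a = (T − W)/m and b = T/m:

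- share undated: q = (m/W)(e^−a − e^−b)
- part of the mean lost with those events: A = (m²/W)[(a + 2)e^−a − (b + 2)e^−b]
- reported mean: (m − A)/(1 − q)

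Inputs: the extension lasts 48 weeks, or 336 d (SAP 1.1.1). T = 672 d is an assumption (48 + 48 weeks, reading V11/Week 48 in SAP 2.3.4 as the extension start counted from baseline), because the period limits in SAP 2.5.1 are redacted. W = 90 d, the distributions and the means are also assumptions.

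For m = 180: a = 582/180 = 3.233 and b = 672/180 = 3.733. Then q = 2 × (0.0394 − 0.0239) = 3.1%, A = 360 × (5.233×0.0394 − 5.733×0.0239) = 24.9 d, and the reported mean is (180 − 24.9)/0.969 = 160 d.

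For a mixture of 90% with mean 14 d and 10% with mean 365 d, the true mean is 0.9×14 + 0.1×365 = 49.1 d. Only the long component loses events: a = 1.5945, b = 1.8411, q = 0.1 × (365/90) × (0.2030 − 0.1586) = 1.8%. Its A is about 178 d, so the reported mean is (49.1 − 17.8)/0.982 = 31.9 d.

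| Case (T = 672, W = 90) | Undated | Reported mean | True mean |
|---|---|---|---|
| m = 30 d | 0.0% | 30.0 d | 30 d |
| m = 90 d | 0.1% | 89.4 d | 90 d |
| m = 180 d | 3.1% | 160 d | 180 d |
| Mixture | 1.8% | 31.9 d | 49.1 d |

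If half of the undated events are later dated, the m = 180 mean becomes 168 to 170 d and the mixture mean 38 to 41 d. The mixture median hardly moves: 11.0 d against a true 11.3 d.

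Upper sensitivity only, T = W = 336 d: 8.9% undated and 27.1 d reported for a true 30 d, rising to 45% and 82 d for a true 180 d. This spreads onset over an extension in which no treatment is given (Protocol 6.3) and allows no post-study stop dates.

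**The case against.** The strongest reply is that this concerns presentation and the information is not lost. The SAP states its rule openly, safety is descriptive in about 60 subjects, and nothing is decided on duration. Event counts and listings retain every undated event. Where each subject has one event per PT, the number of subjects in the duration table set against the related-event count already shows the gap. The unseen table formats may contain a row for ongoing events, and Protocol 10.5 is not visible either. All of this stands and limits the weight of the point. It does not change what SAP 2.5.1 specifies for the duration summary.

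The size is also assumed. Short events with early onset give almost no bias. The mixture needs a tenth of events to average a year. Even then, with 1.8% undated and 20 independent events, the chance that none is undated is 0.982^20, about 70%. The median is reported beside the mean. The sensitivity figures disregard the follow-up in Protocol 7.2.6 and should be read only as an outer limit. These points are fair, and they are a reason to print the count: a zero there would settle the matter.

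Finally, a minimum observed duration does not remove the bias. Under the 336-day sensitivity, counting unresolved events at that minimum moves the mean only from 82.0 to 98.5 d against a true 180 d. That is correct. It is why the fix asks for the count and the minimum to be displayed, not for a replacement estimate.

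**Conclusion.** The concern holds as stated. As written, SAP 2.5.1 limits the duration summary to related AEs with a recorded stop date and specifies neither a count nor a minimum length for the others. The summary is expected to understate duration if any related AEs are unresolved; in a given data set this is certain only when the ongoing events have already lasted longer, on average, than the dated ones. The effect ranges from nothing to a substantial shift in the mean (31.9 d reported against 49.1 d in the assumed mixture), with the median far less affected there. Where this trial falls cannot be known from the documents. The direction rests on stop dates being missing because events are unresolved, not because of recording gaps. Incidence, severity and event counts are untouched.

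**What to change.** In SAP 2.5.1, keep the no-imputation rule and add:

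1. Stop dates recorded on the AE follow-up form are used where available by database lock.
2. Beside each duration summary for related AEs, give by SOC and PT the number and percent of events ongoing or without a stop date. Separate ongoing from resolved with unknown date where the data allow. Show the minimum observed duration of ongoing events, from start date to last visit or last recorded follow-up date.
3. Label the statistics as *events with a recorded stop date*.

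Optionally, add one Kaplan-Meier median pooled over all related AEs with ongoing events censored, noting repeated events within subject and the assumption of non-informative censoring. By PT it would often not be estimable in about 60 subjects.

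The cost is SAP wording, one derivation (an ongoing flag and minimum observed duration) and extra table columns. The last visit can serve as the end point: it is already listed for withdrawn subjects, and attendance is summarised by scheduled visit. A contact date after the study is not shown to be collected, so a later date applies only where the follow-up form records one. The downside for the sponsor is that reported durations may look longer.

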2.5.2 Subgroup analyses

Subgroup analyses will be performed for adverse events (number and percent of subjects with related adverse events as well as number of events by SOC, PT, and severity) on subgroups defined by study center and FST group (I-III, IV, and V-VI) respectively.

2.6 Interim Analysis

No interim analysis is planned.

2.7 Changes in the Analysis Planned in the Protocol

There have been no substantial changes from the statistical methods described in the protocol.

Statistical Analysis Plan, Version 1.0 FINAL, 10 AUG 2020

3 Reference List

There are no other references beyond those that are included in the protocol.

Statistical Analysis Plan, Version 1.0 FINAL, 10 AUG 2020

Effective

SIGNATURES PAGE

Date	Signed by
[REDACTED]	[REDACTED]
202[REDACTED]	[REDACTED]
[REDACTED]	[REDACTED]

Effective
